This statistical analysis plan is prepared for the “A Phase I, Randomized, Double-Blind, Placebo-Controlled Study to Evaluate the Safety, Tolerability, and Pharmacokinetics of Single and Multiple Ascending Doses of Inhaled MBS-COV (SNS812) in Healthy Participants” (Protocol No.: SNS812CLCT01) of Oneness Biotech Co., Ltd. In this document, the contents and methods of statistical analysis will be described in detail.

This statistical analysis plan is drafted based on protocol of SNS812CLCT01 (version 4.1, 19Jan2023) and Case Report Form (CRF, version 2.0, 09Jan2023).

2. Study Objectives

2.1. Part A: SAD phase

2.1.1. Primary Objectives

- To determine the safety and tolerability of MBS-COV after single doses in healthy participants.

2.1.2. Secondary Objectives

- To evaluate the pharmacokinetics (PK) of MBS-COV after single dose administration in healthy participants.
- To evaluate the immunogenicity of MBS-COV.

2.2. Part B: MAD phase

2.2.1. Primary Objectives

- To determine the safety and tolerability of MBS-COV after multiple doses in healthy participants.

2.2.2. Secondary Objectives

- To evaluate the pharmacokinetics (PK) of MBS-COV after multiple dose administrations in healthy participants.
- To evaluate the immunogenicity of MBS-COV.

3. Study Design

This is a Phase I, randomized, double-blind study designed to evaluate the safety, tolerability and pharmacokinetics (PK) of inhaled MBS-COV in healthy adult participants in the part A and part

B of the study. A total of 44 male and female healthy participants will be enrolled. All participants, after signing the Informed Consent Form (ICF), will be assessed during the screening phase. Only those participants who successfully complete the screening phase and meet the study eligibility criteria will be enrolled. MBS-COV will be administered via inhalation through a portable mesh nebulizer.

3.1. Part A: SAD phase

Part A includes 3 dose-escalation cohorts (0.3 mg/kg, 0.6 mg/kg, 1.2 mg/kg MBS-COV or placebo). Each cohort will include 8 participants (6 active and 2 placebo) per below table:

| Cohort | MBS-COV Does Active:placebo | Frequency of Does |
|--------|--------------------------------|-----------------------|
| A1 | 0.3 mg/kg (6:2) | Single Administration |
| A2 | 0.6 mg/kg (6:2) | Single Administration |
| A3 | 1.2 mg/kg (6:2) | Single Administration |

From the perspective of safety, sentinel dosing will be used in each cohort, and the first 2 subjects in each cohort will be randomized 1:1 to MBS-COV or placebo. If the dose can be well tolerated for 48 hours after full administration per the study Safety Review Committee (SRC) consisting of the sponsor (designee), site Principle Investigator, and medical monitor, the remaining 6 subjects in the cohort may be randomized 5:1 to MBS-COV or placebo.

All participants will have a screening visit within 28 days of check-in (Day -1) to determine eligibility. Eligible participants will be admitted to the study center on study Day -1 at which point their eligibility to participate in the study will be confirmed. Only those participants who successfully complete the screening phase and meet the study eligibility criteria will proceed to be randomized to receive a single dose of MBS-COV or placebo in the morning of Day 1 at the assigned dose.

The decision for cohort (dose level) escalation to the higher dose levels will be made by the study SRC after safety review of available information 7-day post treatment period. The data from SAD phase will be reviewed for safety trends to start MAD phase.

3.2. Part B: MAD

This is a randomized, double-blind, placebo-controlled study in approximately 20 healthy participants. Doses will be selected based on a comprehensive review of the SAD data and estimates of the clinically efficacious dose.

The MAD Phase of the study consists of a screening period followed by multiple dose administrations of MBS-COV or placebo through a portable nebulizer once daily for 7 consecutive days (Day 1 to Day 7). Participants will be followed up for 21 days to assess post-treatment safety.

The decision for the escalation to the higher dose levels will be made by the study SRC after safety review of available information 7-day post treatment period. Each cohort will include ten participants (8 active and 2 placebo) per table below:

| Cohort | MBS-COV Does Active:placebo | Frequency of Does |
|--------|--------------------------------|-----------------------|
| B1 | 0.6 mg/kg (8:2) | Once daily for 7 days |
| B2 | 1.2 mg/kg (8:2) | Once daily for 7 days |

4. Study Outcomes Measures

4.1. Part A: SAD Phase

4.1.1. Primary Outcomes Measures

The primary outcome measures in this study are:

- Evaluation of the safety and tolerability of MBS-COV after a single administration in healthy participants. The following parameters will be used to assess safety:
 - Incidence and severity of Treatment-Emergent Adverse Events (TEAEs)
 - Incidence of withdrawals due to Adverse Events (AEs)
 - Incidence of Treatment-Related Adverse Events
 - Incidence of Serious Adverse Events (SAEs)
 - Change/shifts in laboratory values from baseline
 - Change in vital signs including blood pressure, pulse, respiratory rate, and temperature from baseline
 - Change in spirometry from baseline to assess the acute bronchospasm

- Change in other safety examination parameters from baseline

4.1.2. Secondary Outcome Measures

The secondary outcome measures in this study are:

Pharmacokinetic Outcome Measures:

- Maximum observed plasma drug concentration (C_{max})
- Apparent terminal elimination half-life ($t_{1/2}$)
- Time to maximum observed plasma drug concentration (T_{max})
- Area under the plasma drug concentration-time curve (AUC) from time 0 to the time of the last quantifiable concentration (T_{last}) (AUC_{0-t})
- AUC from time 0 to infinity ($AUC_{0-\infty}$)
- Apparent plasma clearance (CL/F)

Immunogenicity Outcome Measure:

- Occurrence of anti MBS-COV antibody after administration of MBS-COV

4.2. Part B: MAD Phase

4.2.1. Primary Outcomes Measures

The primary outcome measures in this study are:

- Evaluation of the safety and tolerability of MBS-COV after multiple dose administrations in healthy participants. The following parameters will be used to assess safety:
 - Incidence and severity of Treatment-Emergent Adverse Events (TEAEs)
 - Incidence of withdrawals due to Adverse Events (AEs)
 - Incidence of Treatment-Related Adverse Events
 - Incidence of Serious Adverse Events (SAEs)
 - Change/shifts in laboratory values from baseline
 - Change in vital signs including blood pressure, pulse, respiratory rate, and temperature from baseline
 - Change in spirometry from baseline to assess the acute bronchospasm
 - Change in other safety examination parameters from baseline

4.2.2. Secondary Outcome Measures

The secondary outcome measures in this study are:

Pharmacokinetic Outcome Measures:

- Maximum observed plasma drug concentration (C_{max})
- Apparent terminal elimination half-life ($t_{1/2}$)
- Time to maximum observed plasma drug concentration (T_{max})
- Area under the plasma drug concentration-time curve (AUC) from time 0 to the time of the last quantifiable concentration (T_{last}) (AUC_{0-t})
- AUC from time 0 to infinity ($AUC_{0-\infty}$)
- Apparent plasma clearance (CL/F)
- Estimate of steady state Pharmacokinetic Parameters such as AUC_{0-t} , and $C_{max,ss}$, $C_{min,ss}$, C_{avg} , T_{max} , $t_{1/2}$, AUC_{tau} , λ_z , CL_{ss}/F , V_{ss}/F , DF, AR_{AUC}/AR_{Cmax} (accumulation ratio) for multiple dose administration of MBS-COV

Immunogenicity Outcome Measure:

- Occurrence of anti MBS-COV antibody after administration of MBS-COV

4.3. Study Safety Outcome Measures

4.3.1. Adverse Events

Adverse Events (AE)

An adverse event (AE) is defined as any unfavorable or unintended sign, symptom, or disease that occurs or is reported by the participant to have occurred, or a worsening of a pre-existing condition. An adverse event may or may not be related to the study treatment.

AEs will be elicited through direct questioning and participant reports. Any abnormality in physical examination findings or laboratory results that the investigator believes is clinically significant (CS) to the research participant and that occurred after initiation of the first study treatment will be reported as AEs. Abnormal findings that are NOT clinically significant should not be recorded as an AE.

Serious Adverse Events (SAE)

A SAE is defined as any AE that:

- Results in death
- Is life threatening (the participant is at immediate risk of dying from the adverse experience)
- Requires participant hospitalization or prolongs existing hospitalization

- Results in persistent or significant disability/incapacity
- Is a congenital anomaly/birth defect
- Important medical events that may not result in death, be life-threatening, or require hospitalization may be considered a serious adverse effect when, based upon appropriate medical judgment, they may jeopardize the participant or participant and may require medical or surgical intervention to prevent one of the outcomes listed in this definition.

Treatment - Emergent Adverse Event (TEAE)

Any adverse event which occurs on or after the first administration of study drug are defined as TEAE, namely if date/time of AE occurrence is greater or equal to the date/time of first dose, those AEs will be judged as TEAE (rising grade in severity will be recorded as a new AE in CRF). For this study, AE will be collected start from the first study drug administration. Therefore, all AEs will be TEAEs.

AE Leading to Treatment Discontinuation

In this study, these AEs caused subject treatment discontinuation.

AE Leading to Death

In this study, these AEs caused subject death.

Treatment Related Adverse Event

The PI's (or designee's) assessment of an AE's relationship to study drug is part of the documentation process. The evaluation of relationship is based on the following 5 levels: Definitely related, Probably related, Possibly related, Unlikely related, Unrelated and will be recorded on CRF. The adverse events been evaluated the relationship to drug as Definitely related, Probably related, Possibly related will be referred to treatment related adverse event. The detailed definition and guidelines of 5 level relationship (Definitely related, Probably related, Possibly related, Unlikely related, Unrelated) of adverse event to study drug can be referred on protocol section 9.2.3.

Grading AE by Severity

According to the guideline of "Toxicity Grading Scale for Healthy Adult and Adolescent Volunteers Enrolled in Preventive Vaccine Clinical Trials" issued by FDA, the severity of adverse events occurred in this study will be graded. The general guidelines for assessing the AE

grade refer on protocol appendix 1.

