9.2. REPORTING OF ADVERSE EVENTS (AEs)

The Investigator will then record all relevant AE/SAE information in the eCRF. All AEs will be collected from the time of dose administration until the safety follow-up visit. Medical occurrences that occur before the start of the study treatment, but after obtaining the ICF will be recorded in the Medical History section of the eCRF and not in the AE section, unless considered related to the study procedures. All events will be followed to resolution or until the participant completes the study. A final assessment of outcome will be made at that time.

All AEs must be recorded in the participant's medical records and on the CRF. AEs will be reported using customary medical terminology along with the following information: the onset and end dates, whether the event is considered to be a SAE (see [Section 9.3](#)), the impact the event had on study treatment (see [Section 9.2.1](#)), the Toxicity Grading Scale (intensity) of the event (see [Section 9.2.2](#)), the causality of the event (see [Section 9.2.3](#)), whether treatment is given as a result of the event (see [Section 9.2.4](#)), and the outcome of the event (see [Section 9.2.5](#)).

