

16. APPENDIX**16.1. APPENDIX 1: TOXICITY GRADING SCALE FOR HEALTHY ADULT AND ADOLESCENT VOLUNTEERS ENROLLED IN PREVENTIVE VACCINE CLINICAL TRIALS**

For complete detailed information please refer to the link below:

<https://www.fda.gov/media/73679/download>

A. Tables for Clinical Abnormalities

Local Reaction to Injectable Product	Mild (Grade 1)	Moderate (Grade 2)	Severe (Grade 3)	Potentially Life Threatening (Grade 4)
Pain	Does not interfere with activity	Repeated use of non-narcotic pain reliever >24 hours or interferes with activity	Any use of narcotic pain reliever or prevents daily activity	Emergency room (ER) visit or hospitalization
Tenderness	Mild discomfort to touch	Discomfort with movement	Significant discomfort at rest	ER visit or hospitalization
Erythema/Redness *	2.5 – 5 cm	5.1 – 10 cm	> 10 cm	Necrosis or exfoliative dermatitis
Induration/Swelling **	2.5 – 5 cm and does not interfere with activity	5.1 – 10 cm or interferes with activity	> 10 cm or prevents daily activity	Necrosis

* In addition to grading the measured local reaction at the greatest single diameter, the measurement should be recorded as a continuous variable.

** Induration/Swelling should be evaluated and graded using the functional scale as well as the actual measurement.

Vital Signs *	Mild (Grade 1)	Moderate (Grade 2)	Severe (Grade 3)	Potentially Life Threatening (Grade 4)
Fever (° C) ** (° F) **	38.0 – 38.4 100.4 – 101.1	38.5 – 38.9 101.2 – 102.0	39.0 – 40 102.1 – 104	> 40 > 104
Tachycardia - beats per minute	101 – 115	116 – 130	> 130	ER visit or hospitalization for arrhythmia
Bradycardia - beats per minute***	50 – 54	45 – 49	< 45	ER visit or hospitalization for arrhythmia
Hypertension (systolic) - mm Hg	141 – 150	151 – 155	> 155	ER visit or hospitalization for malignant hypertension
Hypertension (diastolic) - mm Hg	91 – 95	96 – 100	> 100	ER visit or hospitalization for malignant hypertension

Hypotension (systolic) – mm Hg	85 – 89	80 – 84	< 80	ER visit or hospitalization for hypotensive shock
Respiratory Rate – breaths per minute	17 – 20	21 – 25	> 25	Intubation

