7.2. Data Handling

7.2.1. Missing Data

Data evaluation will be based on the data collected by CRF without any imputation for safety part. If the categorical data is missing, it can be recorded as “missing” or “unknow”.

The missing date of AE will be imputed as follows. The imputation of missing date of AE is only used to classify AEs, and the original missing date record will still be presented when generating the listing of AE related data.

- If the start date of AE was missing
 - 1) If year and month were known and earlier than that of the first treatment dose, then impute with the last day of the known month.
 - 2) If the year and month were known as same as that of the first treatment dose, then impute the start date with the date of first treatment dosing (date in form of “XXX(Day)XXX(Month)”).
 - 3) If year and month were known and later than that of the first treatment dosing, then impute with the first day of the known month.
 - 4) If year only was known and earlier than that of the first treatment dosing, then impute date with “31Dec”.
 - 5) If year only was known and equal to that of the first treatment dosing, then impute the start date of AE as the first treatment dosing date (date in form of “XXX(Day)XXX(Month)”).
 - 6) If year only was known and later than that of the first treatment dosing, then impute with “1st JAN”.
 - 7) If year, month and day were all missing, use the first treatment dosing date as the start date of AE.
 - 8) Other conditions will be regarded as missing.
- If the end data of AE was missing
 - 1) If year and month were known, then impute with the last day of the known month.
 - 2) If year only was known, then impute with “31Dec”.
 - 3) If the start date was later than the end date after imputation, then use the start date directly as the end date.
 - 4) Other condition will be regarded as missing.

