7.2.2. Derivation and Transformation on Data

Apart from the calculation of study endpoints mentioned in section 4, which are based on data collected via CRF, no derivation or transformation will be done for data. Outliers will be reported to data management function as data issue to be resolved or confirmed before database lock. No other special data handling will be done.

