7.4.2. Adverse Events

All AEs will be coded and classified according to the MedDRA (version refer to DMP) with System organ class (SOC) and Preferred Term (PT).

Frequencies and percentages of subjects and frequencies of events by treatment group for all adverse events will be summary as following:

- Summaries of all AE
- Summaries of all AE by SOC and PT
- Summaries of all SAE by SOC and PT
- Summaries of all Treatment related Adverse Event by SOC and PT
- Summaries of all AE leading to early discontinuation by SOC and PT
- Summaries of all SAE leading to early discontinuation by SOC and PT
- Summaries of all Treatment related Adverse Event leading to early discontinuation by SOC and PT
- Summaries of all AE by SOC and PT and the Worst Severity
- Summaries of all Treatment related Adverse Event by SOC and PT and the Worst Severity

Listing by subjects will be provided for all AEs, SAE, Treatment related Adverse Event.

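### Each rise in grade becomes a new AE record and nothing rejoins the records, so one worsening episode counts as two to four events in the SAP's event columns

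*SAP*

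**What the plan says.** **Recording.** In its definition of a treatment-emergent AE, SAP 4.3.1 says that a "rising grade in severity will be recorded as a new AE in CRF".

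**Counting.** SAP 7.4.2 opens its list of AE tables with "Frequencies and percentages of subjects and frequencies of events by treatment group for all adverse events will be summary as following". Each table therefore carries a subject column and an event column. The list includes "Summaries of all AE by SOC and PT and the Worst Severity", and the same for treatment-related AEs.

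**Derivation.** Apart from calculating the endpoints in its Section 4, SAP 7.2.2 says that "no derivation or transformation will be done for data". Section 4 has no rule for linking AE records, and neither has 7.4.2.

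**Causality.** SAP 4.3.1 treats an AE as treatment-related if it was assessed as definitely, probably or possibly related. SAP 7.2.1 says: "Data evaluation will be based on the data collected by CRF without any imputation for safety part". The one exception it makes is for AE dates. On missing categories it says "If the categorical data is missing, it can be recorded as" missing or unknown. No rule says how an AE without a causality assessment enters the related-AE tables.

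**The concern.** The recording rule is reasonable in itself, because it keeps the date of each change in grade. It needs a matching counting rule, and the SAP has none. Applied as written, the event column counts records and not episodes. A reader of the report would take it as the number of times something happened. Here it is that number plus the number of times something got worse, and the two cannot be separated from the table.

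Arms are small, at six or eight active and two placebo per cohort, so a few extra records change an event total visibly. Extra records arise only where events worsen. An arm with the same number of episodes but more worsening would therefore show more events.

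The causality gap is separate and smaller. Incidence of treatment-related AEs is one of the primary outcome measures, and an AE with no assessment would be left out of it without any stated decision to do so.

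**Working it through.** **Inputs**

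- One new record per recorded rise in grade: SAP 4.3.1.
- Table contents are subjects (n and %) and events (n): SAP 7.4.2.
- Grades 1 to 4: Protocol Appendix 1, adopted by SAP 4.3.1. An episode that only worsens has at most three rises.
- Arm sizes are 6 active and 2 placebo per Part A cohort (SAP 3.1), and 8 active and 2 placebo per Part B cohort (SAP 3.2).

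The plan gives no figure of its own to reproduce on this point.

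**Records from one worsening episode**

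Records = 1 + recorded rises = number of distinct grades recorded. The possible worsening-only paths are the ways of choosing two, three or four of the four grades:

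| Grades recorded | Number of paths | Events counted | Subjects counted |
|---|---|---|---|
| 2 | C(4,2) = 6 | 2 | 1 |
| 3 | C(4,3) = 4 | 3 | 1 |
| 4 | C(4,4) = 1 (Grades 1-2-3-4) | 4 | 1 |

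That is 11 paths, all giving two to four events. A parameter with no Grade 4, such as cholesterol, gives at most three. An episode that falls and rises again could give more than four.

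**Effect on a table**

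Events tabulated = episodes + recorded rises, so relative inflation = recorded rises / episodes. The documents give no worsening rate, so the following is an assumed illustration: 5 episodes in 4 of 8 subjects, with one episode worsening.

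| Recorded rises | Events tabulated | Inflation | Subjects |
|---|---|---|---|
| 0 | 5 | 0/5 = 0% | 4/8 (50%) |
| 1 | 6 | 1/5 = +20% | 4/8 (50%) |
| 2 | 7 | 2/5 = +40% | 4/8 (50%) |
| 3 | 8 | 3/5 = +60% | 4/8 (50%) |

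The subject column does not move, because a subject counts once however many records there are. Worst severity does not move either, because the highest grade over the split records is the highest grade of the episode. The worst-severity tables give no rule for their own event column, so they do not solve the problem.

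**Missing causality**

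One participant whose only possibly related AE lacks an assessment changes related-AE incidence by 1/6 = 16.7 percentage points in a Part A active arm, or 1/8 = 12.5 in a Part B active arm.

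**The case against.** The best reply is that the measures that matter are untouched. The primary outcomes are incidence and severity. Incidence is read from subjects, severity from the worst grade, and both are right under the split. The event column stands beside the subject column, no inferential statistics are planned, and extra records overstate toxicity in the arm whose events worsen. All of this stands, and it limits the weight of the point. It does not make the event column correct.

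It can also be said that the parenthesis in SAP 4.3.1 covers only conditions present before dosing that worsen afterwards. The text has no such limit. The AE definition in the same section already includes worsening of a pre-existing condition, so the parenthesis would then add nothing.

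Some stronger readings are tempting and are not supported:

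- **Distorted durations and outcomes.** Neither SAP 7.4.2 nor Protocol 8.7.8.1 plans a table of AE duration or outcome.
- **The lower-grade record is closed as if the event had ended.** The documents do not say so. It depends on the CRF and its completion rules, which are not among them.
- **Conflict with Protocol 9.2.** That section lists the items to record for each AE and says "All events will be followed to resolution or until the participant completes the study". It does not require one record to span every change of grade.
- **Missing causality is classed as unrelated.** No such rule or table exists. The AE would be absent from the related tables but present in the all-AE tables and the listing. Protocol 9.2 and 9.2.3 require an assessment for every AE, so missing values should be few.

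**Conclusion.** The point holds for the event columns of SAP 7.4.2. Under the rules as written, an episode that only worsens is counted two to four times. This rests on each rise being recorded as SAP 4.3.1 says, and on no linking step outside the documents. The total inflation depends on how often events worsen, which cannot be known in advance. The +20% to +60% figures are an illustration and not a forecast.

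A reader might infer that the active-placebo safety comparison as a whole is biased. The documents do not support that, because subject incidence and worst severity are unaffected and the analysis is descriptive.

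The causality gap is secondary. It follows from reading SAP 4.3.1 and 7.2.1 together, and it matters only if an assessment is still missing at database lock.

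**What to change.** **SAP 7.4.2.** State that records representing grade changes of one continuous episode count once in the event columns, at maximum grade. Identify them as follows:

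1. Use a link or parent-AE number on the CRF, if one exists.
2. Otherwise, require the same preferred term in the same participant, with the later record at a higher grade and starting on the recorded end date of the earlier one. Imputed end dates must not be used: SAP 7.2.1 moves a missing end day to the last day of the month, which could make separate events look continuous.
3. Confirm the links at a blinded data review before database lock.

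Keep all records in the listings.

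**SAP 7.2.1.** State that an AE with causality missing at lock counts as treatment-related in the tables, with the raw value kept in the listing.

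**Cost.** Some SAP wording, a small programming step and a short review. There is a small risk of merging true recurrences, for example after successive daily doses in Part B, which would undercount events; the narrow date rule and the review are there to contain it. Related-AE counts rise slightly if any causality is missing.

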4.2.3. Part A (SAD) - Treatment Visit 1: Baseline Visit (T1: Day 1)

The first assigned study treatment dose will be administered after completion of all study evaluations. Adverse events and changes in concomitant medications will be collected. Participants in Cohorts A1 to A3 will be inhaled a single dose of MBS-COV or placebo through a portable nebulizer on Day 1.

The following assessments will be performed:

- Medical history (pre dose)
- Vital signs (pre and post dose) (Vital signs will include blood pressure, pulse, respiration rate, and temperature. On treatment visits will be conducted three times a day, within 120 minutes before administration, within 1 hour after administration, and 4-6 hours after administration, respectively.)
- Randomization (pre dose)
- Physical examination (pre and post dose)
- 12-lead ECG (pre and post dose) (12-lead ECG on treatment visits will be conducted three times a day, within 120 minutes before administration, within 1 hour after administration, and 4-6 hours after administration, respectively.)
- List concomitant medications
- PK timepoints: Cohorts A1 to A3: For the single dose on day 1, blood samples will be collected before dosing, and afterwards at 5 min (± 1 min), 15 min (± 2 min), 0.5 h (± 2 min), 1 h (± 5 min), 2 h (± 5 min), 4 h (± 5 min), 8 h (± 10 min), 10 h (± 10 min) after dosing.
- ADA timepoints: Blood samples will be collected on Day 1 before dosing
- Spirometry Assessment (Spirometry assessments will be started 5 minutes after the dosing with frequent spirometry measurements at 5 (± 1 min), 15 (± 1 min), 30 (± 5 min), 60 minutes (± 5 min).)

- Adverse events evaluation after first dose
- Participants will be confined till 24 hours pharmacokinetic samples are obtained following study drug administration.

4.2.4. Part A (SAD) – Treatment Visit 2 to Treatment Visit 5/End of Treatment (T2: Day 2 to T5: Day 7)

The following assessments will be performed (refer to the schedule of events Table 4-1)

- Vital signs
- Physical examination, including dermatologic examination
- 12-lead ECG
- List concomitant medications
- Laboratory assessments (hematology, chemistry, coagulation and urine analysis) (T2, T3, and T5 only)
- Chest X-ray (T5 only)
- PK timepoints: Cohorts A1 to A3: For the single dose on day 1, blood samples will be collected at 24 h (\pm 10 min) and 48h (\pm 10 min) after dosing.
- Serum pregnancy test only on T5 (EOT)
- Adverse events evaluation

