7.4. MEDICAL HISTORY

A medical history will be recorded during the Screening Phase and will include:

- All ongoing medical conditions
- All previously resolved medical conditions that are relevant in the judgment of the Investigator
- Any prior medical conditions that have resolved within the last year

Events that emerge prior to the first treatment will be recorded in the medical history and not as AEs. Aside from being used to determine participant eligibility, this information will permit the Investigator to record the nature, duration, and severity of any ongoing baseline medical conditions prior to the participant's receiving investigational product treatment.

For each relevant history, the following will be documented:

- Disease/disorder/condition
- Date of diagnosis
- History status (resolved or ongoing).

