8.7.8. Safety Analyses

8.7.8.1. Adverse Events

Adverse events will be classified by system organ class (SOC) and preferred term (PT) according to the most recent version of MedDRA dictionary.

TEAE are defined as adverse events with onset date on or after the first treatment. TEAEs will be summarized by treatment group, System Organ Class, and preferred term. The following TEAE summaries will be provided:

- a) Overall (i.e., regardless of severity or relationship to treatment)
- b) Adverse events by severity
- c) Related adverse events by severity

- d) Adverse events leading to treatment discontinuation by severity
- e) Adverse events leading to death by severity

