4.3.3. Demographics and Baseline Characteristics

Subjects' age (in years, at time of signing informed consent), gender, race, ethnicity, height, weight, and BMI will be recorded on CRF.

A medical history will be recorded on the CRF and will include:

- All ongoing medical conditions
- All previously resolved medical conditions that are relevant in the judgment of the Investigator
- Any prior medical conditions that have resolved within the last year

Events that emerge prior to the first treatment will be recorded in the medical history. Medical history term, duration, and status will be recorded on the CRF

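### The SAP's adverse event tables have no treatment-emergent filter, and its laboratory section plans neither a shift table nor a count of all abnormal results

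*SAP*

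**What the plan says.** **Adverse events.** The incidence and severity of TEAEs is a primary outcome (protocol 2.2.1; SAP 4.1.1 and 4.2.1). For the tables, protocol 8.7.8.1 says "TEAEs will be summarized by treatment group, System Organ Class, and preferred term". SAP 4.3.1 defines a TEAE by comparing the date and time of onset with the first dose, then sets the distinction aside: "For this study, AE will be collected start from the first study drug administration. Therefore, all AEs will be TEAEs". The tables in SAP 7.4.2 are accordingly headed in the form "Summaries of all AE by SOC and PT", and none is restricted to TEAEs.

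The documents differ on events before the first dose:
- Protocol 9.2 says that events after consent and before treatment "will be recorded in the Medical History section of the eCRF and not in the AE section, unless considered related to the study procedures".
- Protocol 7.4 has no such exception: "Events that emerge prior to the first treatment will be recorded in the medical history and not as AEs". SAP 4.3.3 agrees: "Events that emerge prior to the first treatment will be recorded in the medical history".
- The Part A Day 1 visit list has "Adverse events evaluation after first dose", and the Part B Day 1 list is the same.
- SAP 7.2.1 has an imputation rule for AE onsets that begins "If year and month were known and earlier than that of the first treatment dose".

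**Laboratory data.** The primary outcome list in protocol 2.2.1, repeated in SAP 4.1.1 and 4.2.1, names shifts as well as changes in laboratory values. Protocol 8.7.8.2 plans values and changes by time point, and both a listing and a summary of abnormal results, with no restriction to clinically significant ones. SAP 7.4.3 plans by-visit descriptive statistics for values and changes, by-subject listings, a table of clinically significant abnormal results, and pregnancy results.

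**The concern.** The AE tables are sound only if no pre-dose event can reach the AE dataset. Protocol 9.2 leaves that possible for procedure-related events, and screening and Day -1 involve several procedures: blood sampling, swabs and spirometry. Protocol 1.5.3 itself names bruising as a risk of venipuncture. Any such event, once recorded, would be counted in a primary outcome that it does not belong to.

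For laboratory data, no planned table says how many participants were normal at baseline and abnormal after dosing. The AE tables do not fill the gap, because protocol 9.1 and SAP 4.3.1 both keep abnormalities that are not clinically significant out of the AE record. Such a result appears in a listing but is counted as abnormal nowhere. In a first-in-human study, whose dose-escalation criteria name laboratory abnormalities alongside AEs, that count should not rest only on a case-by-case judgment of clinical significance.

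**Working it through.** The plan has no power calculation or other figure to reproduce on this point. The group sizes agree with the stated total: 3 × 8 + 2 × 10 = 44.

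**1. Does the SAP's AE premise hold?** The general rule in protocol 9.2 starts AE collection at dosing, which supports the premise. The exception in the same section does not. Protocol 7.4 and SAP 4.3.3 omit the exception. SAP 7.2.1 says its date imputation serves only to classify AEs. That step has little purpose if every AE is a TEAE by assumption. Whether pre-dose AEs are recorded is therefore unsettled.

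**2. Effect of one misplaced event.** Group sizes come from protocol 8.4. If a dosed participant's only AE is pre-dose, incidence rises by 100/n points:

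| Group | n | Increase (points) |
|---|---|---|
| Part A active, one cohort | 6 | 16.7 |
| Part B active, one cohort | 8 | 12.5 |
| Placebo, Part A pooled (3 × 2) | 6 | 16.7 |
| Placebo, Part B pooled (2 × 2) | 4 | 25.0 |
| Placebo, one cohort | 2 | 50.0 |

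SAP 7.1 does not say whether placebo is pooled, so both forms are shown.

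The documents give no rate for such events. As a range only, with an assumed probability p per participant and independence, the chance of at least one among 44 is 1 − (1 − p)^44:
- p = 0.5%: 19.8%
- p = 1%: 35.7%
- p = 2%: 58.9%
- p = 5%: 89.5%
- p = 10%: 99.0%

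**3. Can the planned laboratory statistics show shifts?** Take n = 6 and an assumed upper limit of normal of 40. Baselines in both data sets are 28, 30, 32, 34, 36 and 38, all normal.

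| | Set 1 | Set 2 |
|---|---|---|
| Post-dose values | 30, 27, 42, 33, 45, 43 | 27, 35, 29, 44, 45, 40 |
| Changes | 2, −3, 10, −1, 9, 5 | −1, 5, −3, 10, 9, 2 |
| Value: mean (SD) | 36.67 (7.607) | 36.67 (7.607) |
| Value: median; min, max | 37.5; 27, 45 | 37.5; 27, 45 |
| Change: mean (SD) | 3.67 (5.279) | 3.67 (5.279) |
| Change: median; min, max | 3.5; −3, 10 | 3.5; −3, 10 |
| Normal to high (above 40) | 3/6 (50.0%) | 2/6 (33.3%) |

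The value mean is 220/6 in both sets. The sum of squares is 8,356 in both, so the SD is √[(8,356 − 220²/6)/5] = 7.607. The six changes are the same numbers in a different order, so every statistic for change agrees. The 16.7-point difference in shifts is invisible in the planned summaries.

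**4. Scope.** SAP 4.3.2 lists 20 biochemistry, 11 hematology and 4 coagulation parameters, 35 in all, to which this applies.

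**5. Abnormal results.** Protocol 8.7.8.2 requires a summary of abnormal results in general. SAP 7.4.3 tabulates only those judged clinically significant, which is a direct narrowing.

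**The case against.** The SAP does not overlook the filter; it gives a reason for leaving it out. Most of the text supports that reason: the general rule in protocol 9.2, protocol 7.4, SAP 4.3.3 and the Day 1 visit lists. Only one clause in protocol 9.2 points the other way. The imputation rules may be standard partial-date handling, and the CRF, which might settle the matter, is not among the documents. If no pre-dose AE is recorded, the AE and TEAE tables are identical. All of that stands and makes the AE part narrow and conditional. It does not make the SAP's sentence safe, since the protocol still permits the case that the sentence rules out.

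On laboratory data, protocol 8.7.8.2 does not ask for a shift table either, so that gap is between the outcome wording and the analysis text in both documents. This is fair: the requirement comes from the primary outcome list, which the SAP adopts but does not carry into 7.4.3. The numerical example is constructed, and with 6 or 8 active participants per cohort a reader could count shifts from the listings. That also stands, so no data are lost. But counting by hand across 35 parameters is not a planned summary of a primary outcome. The objection leaves untouched the narrowing of abnormal results from all to clinically significant only.

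**Conclusion.** The concern holds and should be addressed. The laboratory part is the firmer. The SAP narrows the protocol's summary of abnormal results and has no output for the shift element of a primary outcome. The example shows that the planned statistics cannot stand in for it, under an assumed limit of 40 and n = 6; it does not predict what this trial will find.

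The AE part is real but conditional. It matters only if a pre-dose, procedure-related event is recorded as an AE, and the documents do not say how often that would happen. When it does, a single participant with no later AE moves a group's incidence by 12.5 to 16.7 points in an active group, and by 16.7 to 50 points in placebo, depending on pooling. Separate table shells, if they exist, were not available and might already cover part of this.

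**What to change.** 1. **Pre-dose events.** Reconcile protocol 7.4 and SAP 4.3.3 with protocol 9.2 on whether pre-dose, procedure-related events are AEs.
2. **TEAE flag.** In SAP 4.3.1, delete the statement that every AE will be a TEAE. Apply the date/time definition already given there as a flag, using the SAP 7.2.1 imputed dates where needed. Run the SAP 7.4.2 tables on TEAEs and list any pre-dose AEs separately. This is correct whichever way item 1 is settled.
3. **Laboratory shifts.** Add to SAP 7.4.3 a table of baseline against worst post-dose category by treatment group, using low/normal/high or the protocol Appendix 1 grade where one exists.
4. **Abnormal results.** Add a count of participants with any abnormal result, whatever the clinical-significance judgment, to match protocol 8.7.8.2.

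The cost is SAP wording, one protocol clarification and a few programmed tables. All the data are already collected.
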